It will be followed by an examination of the autonomic nervous system [ANS] functioning and the ANS - central nervous system [CNS] – enteric nervous system [ENS] electrophysiological coupling by using different electrophysiological tools (electrogastrogram [ECG], galvanic skin responses [GSR], photoplethysmography [PPG], breathing belt, electrogastrogram [EGG], electroencephalogram [EEG]). All the electrophysiological recordings will be synchronized and an acclimatization period will be respected. The recordings will be done seated in a quiet room. The physiological measures will ever be recorded at rest (30 minutes, eyes-closed), during a reactivity emotional task (reactivity period) and in the recovery period following the task (30 minutes, eyes-closed). Electrophysiological data will be collected by the acquisition systems BIOPAC® (MP 150, CEROM, France) and BioSemi®. The ECG data will be recorded using 3 single use and adhesive electrodes placed on the inner side of the right wrist, on the right shoulder and on the left side in accordance with the DII standard position (Einthoven). Physiological data recorded are related to the heart rate variability [HRV]. The breathing effects on the HRV will be controlled by means of the breathing rate recording using a breathing belt. The GSR data will be recorded using 2 skin sensors placed on the third phalanx of the forefinger and of the middle finger of the left hand. Physiological data recorded are related to the cholinergic sympathetic activity (tonic GSR / phasic GSR). The PPG data will be recorded using a finger sensor. Physiological data recorded are related to the adrenergic sympathetic tone and allowing a record of the blood pulse waves associated with the heart rate. The EGG data will be recorded using 6 single use and adhesive electrodes placed on the skin of the abdomen. Physiological data recorded are related to the gastric electrical activity. The EEG data will be recorded using a EEG headsets including 64 electrodes. The EEG is related to the brain activity generated by the neural functioning. The emotional reactivity task will be explained carefully.

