[figure not shown]
¹ The bloc 1 will not be included in the final statistical analysis because is considered as a training bloc. This choice in accordance to the potential biases related to the increase of the sympathetic activity at the beginning of the task caused by a simple moving to action following the resting period.

second session, a short training session of the biofeedback [BFB] technique will be done and the software using for the biofeedback training will be supplied to each participant included in the experimental group to allowed to us to practice BFB by their self at home. The installation of the program and the explanations needed for using it, will be done during the second session (T2). The BFB software (Emwave Pro®) includes a photoplethysmography sensor that can be positioned on the earlobe. The participants will have to practice the biofeedback technique the next 24 days (3X5 min/day).

The period (24 days) between the second session and the third session (T2-T3) will be considered as the intervention period. At the end of the second session (T2), the participants will be separated into two inter-subject groups: an experimental group performing BFB technique (3X5 min per day) in the intervention period (T2-T3) and a control group not performing a specific exercise in the intervention period (T2-T3). The first 40 participants (20 IBS / 20 PNES) will be included into the experimental group (BFB training) whereas the last 10 participants (5 IBS / 5 PNES) will be included into the control group (no training). The participants won't be informed of the condition to which they belong. We will measure the parameters of interest before (T2) and at the end of the intervention period (T3). During the intervention period, all the participants will have to answer to online questionnaires (BVAQ-B, LES, DHS) aiming to examine the psychological profile (alexithymia, traumatic events).

The third session (T3), T2 + 24 days, will be similar of the two previous sessions. We will use the same questionnaires and will record the same electrophysiological parameters. Finally, a debriefing will be done at the end of the session for each participant. The session will be considered as the end of the study visit.

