Concerning the online questionnaires: the package 1 is constituted by the SSQ6, the MAIA-2 and the STAI Y-B. The package 2 is constituted by the Brief-Cope, the BFI-N and the CTQ. The package 3 is constituted by the DHS. The package 4 is constituted by the BVAQ-B and the LE

II : Statistical analysis plan

Independent variables

Analysis A:

The participants will be separated into two inter-subject groups:

- An experimental group performing BFB technique in the intervention phase (T2-T3)
- A control group no performing an exercise in the intervention phase (T2-T3)

The participants won't be informed of the condition to which they belong.

Independent variables

- Measurement time (T1 / T2 / T3) intra-subject
- Group (experimental group / control group) inter-subject

Analysis B:

The participants will be separated into two inter-subject groups performing by a cluster analysis (HF or RMSSD) in the first session (T1):

- A dysfunctional neurovegetative profile (low vagal tone + low vagal flexibility) group
- A functional neurovegetative profile (high vagal tone + high vagal flexibility) group

The participants won't be informed about their neurovegetative profile. We will include all the participants.

Independent variable

- Neurovegetative profile (dysfunctional profile / functional profile) inter-subject

Analysis C:

The participants will be separated into two inter-subject groups performing by a cluster analysis (HF or RMSSD) in the first session (T1):

- A dysfunctional neurovegetative profile (low vagal tone + low vagal flexibility) group
- A functional neurovegetative profile (high vagal tone + high vagal flexibility) group

The participants won't be informed about their neurovegetative profile. We will include only the experimental group performing the BFB technique.

Independent variables

- Neurovegetative profile (dysfunctional profile / functional profile) inter-subject
- Measurement time (T2 / T3) intra-subject

Dependent variables

Physiological variables:

ECG –HRV:

- HF (0.15-0.40 Hz – high frequency) frequency-domain parameter
- LF (0.04-0.15 Hz – low frequency) frequency-domain parameter
- LF-0.1 Hertz (0.075-0.108Hz - spectral power of the low-frequency 0.1Hz band) frequency-domain parameter
- LF/HF (ratio of LF to HF power) frequency-domain parameter
- Total power (total power of the 0-0.40 Hertz band) frequency-domain parameter
- RMSSD (root mean square of successive RR interval differences) temporal-domain parameter

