- SDNN (standard deviation of all NN intervals) temporal-domain parameter
- EDR (ECG-derived-respiration)

GSR (tonic GSR / phasic GSR):

- SCR frequency: number of the spontaneous galvanic skin responses by periods
- SCR amplitude: amplitude of the spontaneous galvanic skin responses by periods
- Integrated skin conductance responses [ISCR]: area of the galvanic skin responses identified on the signal

PPG:

- Pulsatility index variation (PI): Transit time flow

Breathing belt:

- Breathing rate by cycles per minute

EGG:

- Dominant power
- Total power [0-0.15 Hertz]
- Slow-waves frequency per minute

EEG:

- Spontaneous brain rhythms: spectral power of the 0-30 Hertz band

Physiological adaptation to the aversive situation (emotional reactivity task):

HRV, GSR and PPG differences will be calculated to measure the physiological changes causing by the task compared to the resting and the recovery periods. The differences will be calculated as follows:

- Physiological reactivity during the task compared to the resting period (Δ = reactivity HRV – resting HRV / Δ = reactivity GSR – resting GSR / Δ = reactivity PPG – resting PPG)
- Physiological recovery following the task (Δ = recovery HRV – reactivity HRV / Δ = recovery GSR – reactivity GSR / Δ = recovery PPG – reactivity PPG)

- Physiological recovery following the task compared to the resting period (Δ = recovery HRV – resting HRV / Δ = recovery GSR – resting GSR / Δ = recovery PPG – resting PPG)

Psychological variables:

- Alexithymia score (BVAQ-B)
- Neuroticism score (BFI-N)
- Trait anxiety score (STAI Y-B)
- Style of coping (Brief Cope)
- Positive affectivity score (PANAS)
- State anxiety score (STAI Y-A)
- Depressive symptoms score (CES-D)
- Perceived-stress level (PSS)
- Coping flexibility + metacoping scores (CFS + VAS)
- Acceptance score (ICQ-18)
- Social support score (SSQ6)
- Interceptive sensitivity score (MAIA-2)
- Life satisfaction score (SWLS)
- Negative impact scores (LES)
- Frequency, severity and intensity scores (DHS)
- Abuse scores (CTQ)

Statistical analyses

All statistical analyses will be performed using IBM SPSS Statistics®, R software® and JASP®. The alpha value for statistical significance will set at $p<0.05$.

Analyses of the scores collected will be done in several stages:

- Highlighting outlier participants to exclude from our statistical analysis.
- All the conditions for application of statistical tests will be verified.

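### EGG total power is taken over 0–0.15 Hz, so as written it counts baseline drift and any breathing below 9 per minute, while the plan states breathing control for HRV only.

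*Combined protocol and SAP*

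**What the plan says.** - **EGG measures.** SAP, Dependent variables, EGG, lists three: dominant power, "Total power [0-0.15 Hertz"], and slow-wave frequency per minute. Only total power has a stated band. No filter, detrending, gastric sub-band, peak-search range or artefact rule is given.
- **Recording.** Study protocol, electrophysiological recordings: "The EGG data will be recorded using 6 single use and adhesive electrodes placed on the skin of the abdomen". The purpose is stated as "Physiological data recorded are related to the gastric electrical activity". Recordings are made during 30 minutes of rest, the task, and 30 minutes of recovery.
- **Breathing.** The same section says: "The breathing effects on the HRV will be controlled by means of the breathing rate recording using a breathing belt". No equivalent statement is made for EGG. The SAP also lists "Breathing rate by cycles per minute" as a dependent variable in its own right.
- **Training.** "The participants will have to practice the biofeedback technique the next 24 days (3X5 min/day"), between T2 and T3. The control group does no specific exercise in that period.
- **Analyses that use EGG.** Analysis A is a repeated-measures ANOVA of time by group on the physiological data. Analysis C compares T2 with T3 in the trained group only. The correlational analysis relates ECG, EGG and EEG. The only covariates named, under Additional analyses, are age and gender.

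**The concern.** A measure meant to reflect gastric activity should respond mainly to gastric activity. This one starts at 0 Hz, where slow baseline drift lies, and ends at 9 cycles per minute, a rate at which a person can breathe. The electrodes are on the abdominal wall, which moves with breathing, and the plan does not say how movement at that frequency would be kept out of the EGG.

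Only one group trains. If training lowered breathing below 9 per minute during the T3 recordings, respiratory power would enter the EGG band mainly in that group and could appear in the Group x Time test as a gastric effect. Analysis C has no untrained comparator at all. Breathing between 2.4 and 9 per minute also falls in the HRV LF band (0.04–0.15 Hz), so one respiratory source could contribute to both signals in the ECG-EGG correlation. Coupling between viscera and brain is the subject of the trial's title, so these results will be read closely.

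**Working it through.** The plan has no computed EGG figure to reproduce. The only stated figure is the band.

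**Step 1: units (Hz x 60 = cycles per minute).**
- EGG total power: 0 x 60 = 0 to 0.15 x 60 = 9.0 per minute.
- HRV LF: 0.04 x 60 = 2.4 to 0.15 x 60 = 9.0 per minute.
- HRV LF-0.1 Hz: 0.075 x 60 = 4.5 to 0.108 x 60 = 6.5 per minute, wholly inside the EGG band.

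**Step 2: respiratory effect.** All signal values here are assumptions, because the documents give none. Take a 30-minute recording with a fixed gastric wave at 0.05 Hz (3 per minute) of amplitude 1, and a breathing sinusoid of amplitude r at the electrodes. The power of a sinusoid is proportional to its squared amplitude. When breathing moves from outside the band to inside it, total power therefore rises by r² relative to gastric power:

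| r | Rise, breathing 15 to 8 or 6 per minute | Change, 15 to 12 or 10 per minute |
|---|---|---|
| 0.1 | 0.1² = 1% | 0% |
| 0.25 | 0.25² = 6% | 0% |
| 0.5 | 0.5² = 25% | 0% |
| 1.0 | 1.0² = 100% | 0% |

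A numerical spectrum summed over 0–0.15 Hz gave the same values. The gastric wave is identical in every row. Other power in the band would make the percentages smaller.

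**Step 3: drift.** Add a linear drift of d gastric-wave amplitudes over the 30 minutes. The ramp has variance d²/12 and the unit wave has variance 1/2, so total power rises by about d²/6: 4%, 17% and 67% for d = 0.5, 1 and 2. The numerical spectrum gave 3.8%, 15.9% and 65.1%. Nothing in the documents suggests that drift differs by group, so this is noise and not a group effect.

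**Step 4: does a narrower band help?** Assume a gastric band of 0.033–0.067 Hz (0.033 x 60 = 2 to 0.067 x 60 = 4 per minute). Absolute power in that band does not include breathing between 4.5 and 9 per minute. A ratio of gastric-band power to power up to 0.15 Hz does not help. If total power rises by 1% to 100%, the ratio falls by 1 − 1/1.01 = 1% to 1 − 1/2 = 50%, again with no gastric change.

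**The case against.** The case against is substantial, and much of it stands.

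- **The causal chain is assumed.** The bias needs training to slow breathing, the slowing to persist outside practice, the rate to fall below 9 per minute, and the electrodes to pick it up. The documents state none of these. Practice is at home, and the protocol gives no instruction to practise during the recorded periods. This stands, and it makes the point conditional.
- **The 0.1 Hz band.** A reader might infer from "LF-0.1 Hertz (0.075-0.108Hz - spectral power of the low-frequency 0.1Hz band) frequency-domain parameter" that the plan expects trained participants to breathe at 4.5 to 6.5 per minute. It does not say so. This is an HRV parameter, and the only analysis planned specifically for it is a correlation with clinical outcomes.
- **Breathing rate is itself tested.** As a listed physiological variable it enters the same ANOVA, so a marked slowing in the trained group could be seen. That is a real safeguard, but it does not remove respiratory power from the EGG, and a mean rate above 9 per minute can hide periods below it.
- **The ECG-EGG correlation need not be inflated.** The planned breathing control of HRV would weaken the shared pathway. Breathing below 9 per minute also leaves the HF band (0.15–0.40 Hz), so a spurious correlation with HF could be negative. The direction is open.
- **The 0 Hz edge may be shorthand.** HRV total power (0–0.40 Hz) and EEG (0–30 Hz) are written the same way, so the list may not be a processing specification. If so, the processing still has to be stated somewhere.

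**Conclusion.** The point holds in conditional form. As written, the measure includes drift, which adds noise, and any breathing below 9 per minute, which can bias the Group x Time and ECG-EGG results if it occurs at T3 mainly in trained participants. Above 9 per minute there is no respiratory effect. The size is unknown: the range of about 1% to 100% rests entirely on the assumed artefact amplitude, and with no EGG variance in the documents the effect on the test cannot be computed.

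Three stronger readings are not supported. A reader might infer that the EGG comparison is biased, but the documents show only that it can be. A reader might infer that drift creates a group difference, but nothing suggests that it differs by group. A reader might infer that dominant power and slow-wave frequency are contaminated too, but no band is stated for them, so all that can be said is that their search range is unspecified. The main criterion is HRV HF, so neither the primary analysis nor the sample size is affected.

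**What to change.** 1. Use absolute power in a pre-stated gastric band as the inferential EGG power measure. About 0.033–0.067 Hz is an example and an assumption for the sponsor to confirm.
2. Detrend the EGG, and set a non-zero lower edge, for example about 0.017 Hz (1 cycle per minute), for total power and for the dominant-peak search.
3. Keep total power as descriptive, and report power outside the gastric band separately.
4. Extend breathing control to EGG with the belt signal. Report, by group and session, the share of recording time with breathing at or below 0.15 Hz. As a sensitivity analysis, repeat the EGG and ECG-EGG analyses with belt-coherent power removed.
5. Do not exclude slow-breathing epochs from the main analysis. Breathing at T3 may be affected by training, so exclusion would select on a post-treatment variable. Do not use a ratio whose denominator extends to 0.15 Hz.

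The cost is SAP wording and a little more processing of signals already recorded. The downside is that activity outside the usual gastric rhythm no longer enters the main EGG test. No change to recording or sample size is needed.

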 - Regressions or the Pearson correlations will be performed in order to measure the inter-signal correlation (ECG-EGG-EEG)
 - Regressions or the Pearson correlations will be performed in order to test our hypothesis about the HF/RMSSD related to the "low vagal tone" profile will be more correlated to Δ HF/RMSSD related to the "low vagal flexibility" profile than to Δ HF/RMSSD related to the "high vagal flexibility" profile. As the same as HF/RMSSD related to the "high vagal tone" profile will be more correlated to Δ HF/RMSSD related to the "high vagal flexibility" profile than to Δ HF/RMSSD related to the "low vagal flexibility" profile

Additional analyses

- We will control the age effect and the gender effect.
- Some additional statistical analyses will be exploratory: stability of the resting and the dynamical neurovegetative endophenotypes before the control period (T1) and at the end of the control period (T2).
- Correlation between the LF 0.1Hz and the clinical outcomes.
- To confirm the physiological effects of the BFB (BFB vs pseudo-BFB) on the flexibility of the electrophysiological coupling concerning the brain-visceral axis.

Sample

Power analysis (G * Power; Faul et al., 2007) was performed to determine a priori the sample size needed for this study. The power analysis, for an ANOVA (repeated measures, within-between factors), was performed for an effect size (η_p^2) of .12 with a power of .95 on the main judgment criterion (HRV – vagal tone HF) and reported a necessary sample of at least 22 participants (Kudo et al., 2014; Paul & Garg, 2012; Wells et al., 2012). We decided to include at least 25 IBS patients SII (20 test & 5 control) and 22 PNES patients (20 test & 5 control) in accordance with the possible inclusion rate and the duration of the study.

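### The only listed EEG variable is the power of one 0-30 Hz band, which as written pools all the rhythms it is named for; separate bands should be prespecified and one named

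*Combined protocol and SAP*

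**What the plan says.** Under Dependent variables, Physiological variables, the SAP has one line for EEG: "Spontaneous brain rhythms: spectral power of the 0-30 Hertz band". It gives no sub-bands, no lower cut-off above zero, no filter or artefact rule, and no choice between absolute and relative power.

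The protocol part states that "The EEG data will be recorded using a EEG headsets including 64 electrodes". Neither part says which electrodes or regions are used or how they are combined.

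The HRV list is more detailed. It has narrow bands with their own limits, such as "HF (0.15-0.40 Hz – high frequency) frequency-domain parameter", and separately a broadband entry, "Total power (total power of the 0-0.40 Hertz band) frequency-domain parameter". The EGG list has dominant power and slow-wave frequency beside its total power.

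EEG is also used elsewhere. Analyses A and C are to be run on the physiological data in general. Under Correlational analysis, "Regressions or the Pearson correlations will be performed in order to measure the inter-signal correlation (ECG-EGG-EEG"). Additional analyses includes an exploratory aim "on the flexibility of the electrophysiological coupling concerning the brain-visceral axis". None of these defines another EEG variable. Under Sample, the main criterion is HRV HF, and the task difference scores cover HRV, GSR and PPG but not EEG.

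**The concern.** The label promises rhythms in the plural; the rule gives one band with one pair of limits. The HRV list shows that the plan writes out sub-bands when it wants them and gives a single wide range when it wants a total. Read the same way, the EEG line is a total-power measure under another name.

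A pooled power cannot tell one rhythm from another. If one rhythm rises and another falls by the same amount, the sum does not move. If only one changes, the change is spread over the whole 0-30 Hz total. This is the only listed brain variable in a study whose title concerns the visceral-brain axis, and it is the only defined EEG candidate for Analyses A and C and for the "inter-signal correlation (ECG-EGG-EEG").

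**Working it through.** The plan states no EEG figure, so there is nothing to reproduce. The calculation below illustrates the dilution under stated assumptions.

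**From the documents:** one band, upper limit 30 Hz, written lower limit 0 Hz.

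**Assumed:** background power density f^-b with b = 1, 1.5 or 2; an added Gaussian peak at 10 Hz with SD 1 Hz and height h = 3 to 10 times the background at 10 Hz; an effective lower limit L of 0.1 or 1 Hz (0.5 Hz is also used for drift).

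**Formulas**
- Background power: B = ln(30/L) for b = 1; otherwise B = (L^(1-b) - 30^(1-b))/(b - 1).
- Peak power: P = h × 10^-b × √(2π).
- Doubling the peak adds P, so the pooled value changes by P/(B + P).

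**Effect of doubling the 10 Hz peak on the pooled value**

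| L | b | B | P (h = 3; h = 10) | Change (h = 3; h = 10) |
|---|---|---|---|---|
| 1 Hz | 1 | 3.401 | 0.752; 2.507 | 18.1%; 42.4% |
| 1 Hz | 1.5 | 1.635 | 0.238; 0.793 | 12.7%; 32.7% |
| 1 Hz | 2 | 0.967 | 0.075; 0.251 | 7.2%; 20.6% |
| 0.1 Hz | 1 | 5.704 | 0.752; 2.507 | 11.6%; 30.5% |
| 0.1 Hz | 1.5 | 5.959 | 0.238; 0.793 | 3.8%; 11.7% |
| 0.1 Hz | 2 | 9.967 | 0.075; 0.251 | 0.7%; 2.5% |

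The range is about 7-42% with a 1 Hz limit and about 1-30% with a 0.1 Hz limit.

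**The same doubling in a separate 8-13 Hz band, b = 1.5.** The background is 2(1/√8 - 1/√13) = 0.152, and the band holds 0.976 of the peak (from -2 to +3 SD). For h = 3 the change is 0.232/(0.152 + 0.232) = 60%. For h = 10 it is 0.774/(0.152 + 0.774) = 84%. These values do not depend on L.

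**Cancellation.** Pooled power is the sum of the band powers, so its change is the sum of their changes. A rise of P in one band and a fall of P in another give zero.

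**Drift.** Let S be the share of pooled power below 1 Hz. A 20% change in that content moves the total by 0.2 × S.
- b = 1.5, L = 0.1: content below 1 Hz is 2(3.162 - 1) = 4.325, so S = 4.325/6.752 to 4.325/6.197 = 64-70%. The move is 13-14%, against 4-12% from doubling the peak.
- b = 1, L = 0.1: content is ln 10 = 2.303, so S = 28-36%. The move is 6-7%, against 12-30%.
- b = 1.5, L = 0.5: content is 0.828 and B = 2.463, so S = 25-31%. The move is 5-6%, against 9-24%.
- L = 1: S is zero.

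Whether drift or the 10 Hz peak matters more therefore depends on b and L, which the documents do not give. Dilution is present in every row of the table.

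**The case against.** The strongest reply is that the line does not say the rhythms are summed. The plural may mean that 0-30 Hz is the range analysed, with the sub-bands left unstated. That reading is possible, but it does not settle the matter: the bands would then be open to choice after the data are seen, and the same correction is needed.

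Several stronger readings are tempting, and the documents do not support them.
- A reader might infer from the written limit of 0 Hz that electrode drift is in the outcome. HRV and EGG total power ("Total power [0-0.15 Hertz"]) use the same notation, and EEG filtering is not described, so this is unknown. Moreover, drift that does not differ between groups adds noise to Analysis A; it does not create a false group-by-time effect.
- A reader might infer that a real change in one rhythm could not be detected. That depends on the variance of the outcome within and between participants, which is not given. A share of power is not a loss of statistical power.
- A reader might infer that the rule yields one number per recording. With 64 electrodes and no combination rule, it does not fix the number of values at all.
- A reader might extend the point to EGG total power. That entry is labelled as a total and stands beside two specific EGG measures, and no calculation supports changing it.

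It also stands that EEG is not the main criterion, that it is outside the task difference scores, and that the plan does not say which EEG feature enters the inter-signal correlation.

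**Conclusion.** The point holds as a weakness in how a secondary outcome is defined. As written, the only listed EEG variable pools all rhythms and cannot separate them, although the same list treats HRV band by band. Under the assumed spectrum, doubling a 10 Hz rhythm moves the pooled value by about 7-42% with a 1 Hz lower limit and about 1-30% with a 0.1 Hz limit. In the b = 1.5 example, the same doubling moves a separate 8-13 Hz band by 60-84%. The slope, peak height, peak width and lower limit are all assumptions. The direction does not depend on drift: with nothing below 1 Hz, the peak is still at most 42% of the pooled total. The main HRV HF comparison is not affected.

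**What to change.** Replace the EEG line in the SAP's list of dependent variables with separate log band powers computed from the same recordings, for example delta 1-4, theta 4-8, alpha 8-13 and beta 13-30 Hz. State the filtering, whether power is absolute or relative, and how the 64 electrodes are combined (which electrodes or regions, and how averaged). Name one band in advance, with the reason for the choice, as the EEG variable for Analyses A and C and for the ECG-EGG-EEG correlation. Label the other bands exploratory.

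The cost is SAP wording and standard spectral processing; no new recordings, visits or participants are needed. The downside is more EEG variables and hence more tests, which naming one band in advance contains.

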- In the case of a failure to respect the conditions for parametric test application, we would make a data transformation to jointly improve normality and homogeneity residues. If the normality is failed and the homogeneity is respected, we would execute non-parametric tests.
- Analysis will be done on the subjects included. Analysis concerning the reactivity period (during the task) will be performed on the all blocs excepted the bloc 1².
- Main and secondary judgment criterions analysis will be performed by parametric tests or by non-parametric tests depending on the conditions for application:

• *Analyse A:*

- An ANOVA to repeated measurement with an intra factor (measurement time: T1 / T2 / T3) and an inter factor (group: experimental / control) on the physiological and psychological data collected.
- Student's test for independent samples will be performed on the psychological scores collected in the second session (T2) to account for the initial level of psychological states between the 2 groups.

² The bloc 1 will not be included in the final statistical analysis because is considered as a training bloc. This choice in accordance to the potential biases related to the increase of the sympathetic activity at the beginning of the task caused by a simple moving to action following the resting period.

- Contrasts will then be made by group on the scores in order to specify the effect of the condition on the physiological and psychological data.
- *Analyse B:*
 - K means non-hierarchical clustering will be performed with K = 2. To categorise participants depending on their resting neurovegetative profile (low vagal tone / high vagal tone) and on their dynamical neurovegetative profile (low vagal flexibility / high vagal flexibility), two K means non-hierarchical clustering will be performed with K = 2. One with HF or RMSSD and one with Δ HF or Δ RMSSD.
 - Student's test for independent samples (dysfunctional neurovegetative profile / functional neurovegetative profile) will be performed on the psychological vulnerability (trait scores) collected.
- *Analyse C:*
 - An ANOVA to repeated measurement with an intra factor (measurement time: T2 / T3) and an inter factor (neurovegetative profile: dysfunctional profile / functional profile) on the physiological and psychological data collected only into the experimental group performing the BFB technique.
- *Correlational analysis:*

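### The SAP names HF as the main criterion but never uses that ranking: one .05 level covers all Analysis A outcomes and contrasts, so about 1 to 5 chance Group x Time findings are expected if biofeedback does nothing

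*Combined protocol and SAP*

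**What the plan says.** Under Statistical analyses, the SAP gives one significance level for everything: "The alpha value for statistical significance will set at" p<0.05. The same section refers once to a ranking of outcomes, in a sentence about the type of test: "Main and secondary judgment criterions analysis will be performed by parametric tests or by non-parametric tests depending on the conditions for application". It does not say there which outcomes are main and which are secondary.

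Analysis A is an ANOVA with three times (T1, T2, T3) and two groups, applied to the physiological and psychological data without naming a subset. By-group contrasts follow. Their number is not given, and they do not depend on a significant interaction.

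The main outcome is named only in the Sample section, to justify the sample size: "effect size (η_p^2) of .12 with a power of .95 on the main judgment criterion (HRV – vagal tone HF"). Resting, task and recovery recordings are all planned, and the SAP does not say which of them supplies this HF value.

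For Analyses B and C the clustering index is left open: "One with HF or RMSSD and one with" the corresponding change score, again HF or RMSSD. The word exploratory is applied only to some of the additional analyses.

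**The concern.** A ranking of outcomes protects the conclusion only if the plan says what follows from it. Here a significant interaction on, say, SCR amplitude or EGG dominant power meets the same criterion as one on HF. No rule says that the claim about biofeedback rests on HF. HF itself could be read at rest, during the task, in recovery or as a difference score.

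With a list this long, some nominally significant results are likely even if the intervention does nothing. A report that followed the plan to the letter could present them on the same footing as the main result. The open choice between HF and RMSSD adds a further decision that could be made after the data are seen.

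**Working it through.** **1. The plan's own figure.** Inputs from the Sample section: partial eta squared .12, power .95, repeated-measures within-between ANOVA. Alpha .05 is from Statistical analyses. The correlation between times is not stated; I assume rho = .5, with sphericity and equal groups.

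- f² = .12 / .88 = .1364, so f = .369.
- Noncentrality = f² × N × m / (1 − rho), where m is the number of times. With N = 22 and m = 3 this is .1364 × 22 × 3 / .5 = 18.0.
- Degrees of freedom: (2 − 1)(3 − 1) = 2 and (22 − 2)(3 − 1) = 40.
- Power = .964.

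The stated minimum of 22 therefore reproduces as the smallest equal-group N for **one** Group x Time test with **three** times. It makes no allowance for further tests.

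**2. Counting the Analysis A outcomes** (Dependent variables; Study protocol).

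- Physiological indices: HRV/ECG 8 + GSR 3 + PPG 1 + breathing 1 + EGG 3 + EEG 1 = 17. EEG is counted as one measure.
- Difference scores: three for each HRV, GSR and PPG index. That is 3 × 12 = 36, or 3 × 11 = 33 if ECG-derived respiration is left out.
- Psychological scores repeated at all three sessions: 8, or 7 if CFS and VAS form one score.
- The nine questionnaires given only once cannot enter a T1/T2/T3 ANOVA and are excluded.

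The SAP does not say how the three recording periods enter the ANOVA, so the total depends on the reading:

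- *Narrow:* each index once, no difference scores. 17 + 7 = 24, or 17 + 8 = 25.
- *Middle:* each index once, with difference scores. 24 + 33 = 57, or 25 + 36 = 61.
- *Wide:* levels also tested in each period (an assumption). 16 × 3 + 33 + 8 = 89 without ECG-derived respiration, or 17 × 3 + 36 + 8 = 95 with it.

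**3. Expected false positives**, one Group x Time test per outcome and no true effect on any. Expected number = n × .05. Chance of at least one, if the tests are independent = 1 − .95^n.

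| Reading | n | Expected | At least one |
|---|---|---|---|
| Narrow | 24-25 | 1.20-1.25 | 71-72% |
| Middle | 57-61 | 2.85-3.05 | 95-96% |
| Wide | 89-95 | 4.45-4.75 | 99% |

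The expected counts need no independence assumption. The last column does, and the outcomes are plainly related: recovery minus rest is the sum of the other two differences, and HF and RMSSD are both used as vagal indices. Those percentages are upper-end approximations. By-group contrasts, Analyses B and C and the correlations are not counted.

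**4. Effect of a fix on power**, same assumptions.

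- HF as sole confirmatory test in the three-time ANOVA: alpha stays at .05 and N = 22 is unchanged.
- A T2-T3 test instead: noncentrality at N = 22 is .1364 × 22 × 2 / .5 = 12.0 and power falls to .909. Power of .95 needs N = 26.
- The Sample section plans 25 IBS and 22 PNES patients (47), while its test and control numbers add to 50. Both exceed 26.
- The 26 assumes equal groups. The planned 40:10 split is worth 4 × 40 × 10 / 50 = 32 equally allocated participants, also above 26.

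**The case against.** The best defence is that a ranking does exist. The analysis section refers to main and secondary criteria, and the Sample section, also part of the SAP, identifies HF as the main one and bases the sample size on it. A single prespecified main outcome needs no adjustment for the others. Many mechanistic studies report secondary outcomes at nominal .05, and a careful reader would discount them.

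Much of this stands. A reader might infer that the plan has no primary/secondary hierarchy, or that every outcome in every analysis is tested alike; the documents support neither. The two references to main criteria rule out the first. As to the second, the Analysis B group comparison is confined to trait scores, once-only questionnaires cannot enter Analysis A, and some additional analyses are called exploratory.

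A reader might also take 95 outcomes as the plan's own count, or expect several false positives as a certainty. The SAP does plan a reactivity-period analysis, so testing by period is plausible, but it nowhere specifies a separate ANOVA for every index in every period. On the narrow count only about one false positive is expected. Nor do the documents give correlations from which an effective number of independent tests could be derived.

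What the defence does not answer is that HF is named without a period or test, and that nothing gives the remaining outcomes and contrasts a different standing.

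**Conclusion.** The concern holds in this limited form: the ranking is mentioned but not put to work. Under no effect, the plan as written is expected to produce between about 1.2 and 4.75 significant Group x Time results in Analysis A, depending on how difference scores and recording periods are handled. About 3 is the figure if the listed difference scores are tested and each index is otherwise tested once.

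This rests on one test per outcome at .05, EEG counted as a single measure, and no true effect on any outcome. It does not show that the HF test is invalid or underpowered: once HF is fixed to one period and one test, that test needs no multiplicity adjustment.

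The algebraic redundancy of the third difference score is not a reason to drop it. Return to baseline is a question of its own, and its test is not determined by the other two.

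**What to change.** In Statistical analyses:

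1. **Name one confirmatory test at .05:** the Group x Time interaction on HF in one stated recording period. Resting HF fits the plan's use of vagal tone for the resting profile. Keeping the T1/T2/T3 ANOVA leaves the basis for N = 22 intact. If a T2-T3 contrast is preferred, restate the power basis (N = 26 under rho = .5 and equal groups, still below the planned 47-50) and give the assumed correlation and allocation.
2. **List the secondary criteria and the number of contrasts.** For all other Analysis A outcomes and contrasts, and for Analyses B and C and the correlations, either control the false discovery rate within stated families (for example, physiological and psychological) or label them exploratory.
3. **Fix the clustering index** for Analyses B and C in advance, HF or RMSSD, with the other as a sensitivity analysis.

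The cost is SAP wording and, if chosen, a p-value adjustment step. Adjustment lowers sensitivity for secondary outcomes; the exploratory label avoids that loss but limits what may be claimed from them. No further data or participants are needed if the three-time HF test is kept.
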